12.1 Determination of sample size

The results of the previous study [Jog 2017, Merz Pharmaceuticals GmbH 2017] suggest that a treatment effect of about one standard deviation might be expected. Assuming a 5% type I error and a randomization ratio of 2:1 a total sample size of 51 analyzable subjects is required to achieve 90% power. In order to account for uncertainty in parameter estimates and drop-outs it has been decided to randomize approximately 75 subjects.

12.2 Analysis sets

The following analysis sets will be defined for the statistical analysis of this study:

Safety evaluation sets

The Safety evaluation set for the unilateral treatment period (SES-UP) includes all subjects who received NT 201 or placebo during the unilateral treatment period.

The Safety evaluation set for the bilateral treatment period (SES-BP) includes all subjects who received NT 201 during the bilateral treatment period.

Full analysis sets

The Full analysis set for the unilateral treatment period (FAS-UP) is the subset of subjects in the SES-UP for whom at least one score of tremor amplitude at wrist level (injected UL) at the study baseline (V2) and at least at one post-baseline score (V3 to V8) during the unilateral treatment period are available.

The Full analysis set for the bilateral treatment period (FAS BP) is the subset of subjects in the SES-BP for whom at least one score of tremor amplitude at wrist level at the Cycle 2 baseline visit (V8) and at least at one post-baseline score (V9 to V11) of both arms during the bilateral treatment period are available.

Per protocol set

The Per protocol set (PPS) is the subset of subjects in the FAS-UP without major protocol deviations. Major protocol deviations will be defined during the blinded data review meeting.

12.3 Endpoints for analysis

12.3.1 Efficacy endpoints

12.3.1.1 Primary efficacy endpoint

Change from study baseline to Week 6 in maximum tremor amplitude measurement at wrist level during the unilateral treatment period.

The maximum angular tremor amplitude at wrist level will be computed in the following three steps:

Step 1: For each of the four tasks and each of the three measurement rounds, described in [Section 9.1.1.2](#), individual 20-second recordings from a kinematic sensor will yield three angular tremor amplitude values for flexion/extension, radial deviation/ulnar deviation and for pronation/supination levels and a single combined Root Mean Square (RMS) angular tremor amplitude value.

Step 2: Calculation of the arithmetic mean from the three measurement rounds of the combined RMS, separately for each task.

Step 3: Among Tasks I to IV selection of the task with the maximum arithmetic mean calculated during Step 2. The amplitudes of this task will be considered as the primary endpoint.

For details on the statistical analysis of the primary efficacy endpoint methods, see [Section 12.4.1.1](#).

12.3.1.2 Secondary efficacy endpoints

12.3.1.2.1 Key Secondary efficacy endpoints

Change from study baseline to Week 6 in TETRAS Performance dominant UL Score (Score no. 5 of [Table 2](#)) in the unilateral treatment period as assessed by the investigator.

Change from study baseline to Week 6 in TETRAS ADL UL score (Score no. 2 of [Table 2](#)) in the unilateral treatment period.

For details on the statistical analysis of the key secondary efficacy endpoints methods, see [Section 12.4.1.1](#).

12.3.1.2.2 Other secondary efficacy endpoints

Unilateral treatment period:

Change from study baseline to Week 6 in TETRAS ADL Functional Impact score (Score no. 3 of [Table 2](#)).

Subject's GICS score of motor dominant UL at Week 6.

Investigator's GICS score of motor dominant UL at Week 6.

Bilateral treatment period:

Change from Cycle 2 baseline to Week 6 in TETRAS Performance dominant UL score (Score no. 5 of [Table 2](#)).

Change from Cycle 2 baseline to Week 6 in TETRAS Performance subscale score (Score no. 4 of [Table 2](#)).

Change from Cycle 2 baseline to Week 6 in TETRAS ADL UL score (Score no. 2 of [Table 2](#)).

Change from Cycle 2 baseline to Week 6 in TETRAS ADL Functional Impact score (Score no. 3 of [Table 2](#)).

12.3.1.3 Other efficacy endpoints

Unilateral treatment period (comparisons NT 201 versus placebo):

Time course of absolute values and change from study baseline to Week 6 of QUEST total score and dimension scores.

Bilateral treatment period

- [Redacted]

- [REDACTED]

[REDACTED]

[REDACTED]

[REDACTED]

[REDACTED]

[REDACTED]

[REDACTED]

[REDACTED]

Subject's GICS score of motor dominant UL at Week 6 of Cycle 2.

Investigator's GICS score of motor dominant UL at Week 6 of Cycle 2.

Time course of absolute values and change from study baseline and Cycle 2 baseline to Week 6 of QUEST total score and dimension scores.

[REDACTED]

12.3.2 Pharmacodynamic endpoints

Not applicable.

12.3.3 Pharmacokinetic endpoints

Not applicable.

12.3.4 Pharmacogenetic endpoints

Not applicable.

12.3.5 Safety endpoints

12.3.5.1 Primary safety endpoint

No primary safety endpoint has been defined.

12.3.5.2 Secondary safety endpoints

The secondary safety endpoint for both the unilateral and bilateral treatment period will be the following:

Incidence of treatment-emergent AEs [TEAEs] related to treatment as assessed by the investigator.

12.3.5.3 Other safety endpoints

Exposure to study treatment by muscle and treated UL for both study periods.

Incidence of TEAEs, TEAEs of special interest [TEAESIs], serious TEAEs, TEAEs leading to discontinuation, and COVID-19 related TEAEs for both study periods.

Time course (i.e., absolute values and changes from respective baseline) during the unilateral treatment period (Cycle 1) in HHD maximum grip strength (in hand of injected UL) and in maximum grip strength difference between both hands.

Time course (i.e., absolute values and changes from respective baseline) during the bilateral treatment period (Cycle 2) in HHD grip strength in both hands.

[REDACTED]

[REDACTED]

Global assessment of tolerability scale as assessed at Week 24 of unilateral treatment period and at Week 12 of bilateral treatment period.

Time course of vital signs (blood pressure, pulse rate) measurement during both study periods.

Time course of body weight measurement during both study periods.

Time course of standard clinical chemistry and hematology parameter measurements during both study periods.

Time course of suicidality assessment during both study periods.

12.3.6 Other endpoints

Other endpoints include subject disposition, demographic data, baseline characteristics, medical history and concomitant diseases, prior and concomitant medication, prior and concomitant non-drug therapies, and [REDACTED]

12.4 Statistical analysis methods

12.4.1 Efficacy endpoints

If not otherwise specified, efficacy analyses of the unilateral treatment period will be based on the observed cases of the FAS-UP. Efficacy analyses of the bilateral treatment period will be based on the observed cases of the FAS-BP.

Adequate descriptive statistics will be provided for all endpoints. Continuous variables (values and changes from baseline) will be summarized by number of non-missing observations, mean, standard deviation, median, quartiles, minimum, and maximum. For qualitative variables, absolute and percent frequencies (number of non-missing observations, %) and, if applicable, shift tables will be displayed. Confidence limits and descriptive p-values will be given, where appropriate.

In the bilateral treatment period it will be distinguished between:

- Category A: endpoints that are general (e.g. TETRAS ADL scores) or applicable to one UL only (e.g. TETRAS Performance subscale dominant UL, TETRAS Performance subscale non-dominant UL); and
- Category B: endpoints that are determined for both ULs (dominant and non-dominant) separately (e.g. TremorTek[®] maximum amplitude).

If not otherwise specified, endpoints in Category B will be summarized by UL (dominant/non-dominant).

12.4.1.1 Primary efficacy endpoint

The primary endpoint (see [Section 12.3.1.1](#)) will be analyzed based on the FAS-UP using least square means from a baseline-adjusted analysis of covariance (ANCOVA) as implemented in SAS PROC MIXED. Fixed factors will be the treatment group (NT 201 versus placebo) and study site. Study baseline angular tremor amplitude at wrist level for the task with the maximum amplitude will be the continuous covariate. Variances will be allowed to differ between treatment groups. This model will be used to test the difference between the treatment groups, NT 201 and placebo ($\alpha = 5\%$, 2-sided). Missing values will not be replaced for the primary analysis.

Sensitivity analyses will comprise:

- Similar model for the PPS;

- Model with treatment-by-site interaction to estimate treatment effects by site;
- Model with additional effects for gender and age; and
- In case, more than 10% missingness occurs in either treatment group, multiple imputation will be conducted as implemented in the FCS statement of SAS PROC MI. Variables considered will comprise maximum tremor amplitude from previous visits including study baseline, treatment, study site, gender, and age.

Study sites might be pooled for statistical analysis. The necessity and details of pooling will be determined under double-blind conditions.

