Descriptive statistics for metric variables will be number of values analyzed (n), number of missing values (nmiss, if any), number of imputed values (nimip, where applicable), mean, standard deviation (SD), median, quartiles, minimum, and maximum. Mean, quartiles, and median will be reported to one decimal place more than the data were collected, for the SD two decimal places more will be displayed; for calculation of derived variables, the number of decimal places is given in the sections below and the number of decimal places to be displayed for descriptive statistics of metric derived variables is defined in [Appendix 8.7](#). For both collected and derived data, descriptive statistics for changes from study / Cycle 2 baseline, as applicable, will be displayed with the same number of decimal places.

⁶ including important and non-important PDs

Frequency tables for qualitative variables will be absolute and percent frequencies (n, %). Frequency tables will include the number of missing values, where applicable. If not specified otherwise, calculation of percentages will be based on all subjects from a specified population and treatment group with non-missing data at the respective visit. The denominator will be specified in a footnote to the tables for clarification if not otherwise obvious. Percentages will be reported to one decimal place.

If not otherwise specified, statistical tests will be conducted 2-sided at type I error rate 5%. P-values will be reported to four decimal places (e.g., $p=0.0375$). P-values below 0.0001 will be presented as '<0.0001'. Confidence intervals (CIs) will be 2-sided for 95% confidence level.

The last valid value before first administration of the investigational product (IP) will be analyzed as study baseline and the last valid value before IP administration in Cycle 2 will be analyzed as Cycle 2 baseline, but only considering data from Cycle 2 baseline visit (V8) and from control visit at Week 18 of Cycle 1 (V7).

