⁸ In the CSP, a model “with treatment-by-site interaction to estimate treatment effects by site” was planned, with the option to pool sites for statistical analysis and the statement that “the necessity and details of pooling will be determined under double blind conditions”. To avoid convergence issues due to the high number of study sites in relation to the number of subjects to be analyzed, it was decided prior to unblinding to pool sites (NoA sites vs. Pol sites) for this interaction analysis. This adaption is thus not considered as a change from analyses planned in the CSP.

⁹ Standard name for variable is ‘sex’ in CDISC SDTM/ADaM.

¹⁰ Note that in case the task with maximum amplitude at wrist level at study baseline cannot be derived due to missing or incomplete assessments of tremor amplitude at wrist level at study baseline, the respective value at Week 6 (V4) cannot be derived either and hence needs to be imputed as well, even if TremorTek measurements of angular tremor amplitude at wrist level are completely available at Week 6 (V4) or not.

¹¹ Maximum tremor amplitude at V3/V4 to be calculated for the task with maximum tremor amplitude at study baseline.

model (as described in Section 4.1.1.1) applied to 1000 completed datasets will be combined for statistical inference. This analysis will be performed on all subjects treated in Cycle 1.

In detail, the following four steps will be performed:

1. One thousand completed datasets will be generated using the FCS statement with the regression method for arbitrary missing data patterns in SAS PROC MI. Variables considered will comprise maximum tremor amplitude at wrist level from previous visits¹², treatment, study site, gender⁹ [female/male], and age [years]. SAS code similar to the following will be used:

```
PROC MI DATA=dataset SEED=602011079 NIMPUTE=1000 OUT=mi_
  MINIMUM=. . . 0 0 0
  ROUND= . . . 1 1 1;
WHERE avisit="Week 6 (V4)" and param="Angular tremor
amplitude at wrist level dominant UL: Task with maximum
amplitude at study baseline";
CLASS SITEID SEX TRT01P;
FCS REG(BASE = TRT01P SITEID SEX AGE);
FCS REG(V3VAL = TRT01P SITEID SEX AGE BASE);
VAR TRT01P SITEID SEX BASE V3VAL AVAL;
RUN;
```

where SITEID = study site
SEX = gender
TRT01P = randomized treatment group
AVAL = maximum tremor amplitude at wrist level at Week 6 (V4)¹³
V3VAL = maximum tremor amplitude at wrist level at Week 4 (V3)¹³
BASE = study baseline value for maximum tremor amplitude at wrist level

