2. The primary endpoint will be calculated from observed and imputed maximum tremor amplitude at wrist level at study baseline and at Week 6 (V4) in the completed datasets.
3. For each completed dataset, the primary endpoint will be analyzed by an ANCOVA model as defined in Section 4.1.1.1 whereby “ods output diffs=diff_mi LSMeans=lsm_mi” will be added to the SAS code.
4. The results from the 1000 imputed datasets will be combined for statistical inference using PROC MIANALYZE. SAS code similar to the following will be used:

¹² including study baseline value for imputation of missing values at Week 4 (V3) and study baseline and Week 4 (V3) values for imputation of missing values at Week 6 (V4).

¹³ calculated using measurements for the task with maximum tremor amplitude at study baseline

```
PROC MIANALYZE data=diff_mi;  
  MODELEFFECTS estimate;  
  STDERR stderr;  
  ODS OUTPUT ParameterEstimates=DIFF_MIAN;  
run;  
  
PROC MIANALYZE data=lsn_mi;  
  BY treatment;  
  MODELEFFECTS estimate;  
  STDERR stderr;  
  ODS OUTPUT ParameterEstimates=LSM_MIAN;  
run;
```

The following statistics will be displayed :

- n (number of values analyzed) and nimp (number of imputed values)
- LS Means of each treatment group (including SE and 95% CI)
- LS Mean treatment difference (including SE, 95% CI, and p-value).

All results from the above-described sensitivity analyses, including any CIs and p-values provided, will be interpreted descriptively only.

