4.1.2 Secondary Endpoints

4.1.2.1 Key Secondary Efficacy Endpoints

The two key secondary efficacy endpoints are defined in Section 2.2.1.2.1 and will be derived as follows:

- The value of the respective TETRAS score (TETRAS Performance dominant UL score and TETRAS ADL UL score) will be calculated for study baseline¹⁴ and for Week 6 (V4) as sum of all corresponding items as defined in Appendix 8.1 (see scores no. 5 and no. 2, respectively).
- Change from study baseline¹⁴ to Week 6 (V4) will be calculated by subtracting the value of the respective TETRAS score at study baseline from the respective value at Week 6 (V4), derived as described above.
- In case an item belonging to the respective TETRAS score is missing, the respective TETRAS score value cannot be meaningfully derived for the affected visit. Hence, derivation of each of the two key secondary endpoints requires that answers to all items belonging to the respective TETRAS score are available at both study baseline and Week 6 (V4). Otherwise, the respective key secondary endpoint will not be calculated and considered as missing.

The two key secondary efficacy endpoints will be tested with ANCOVA models similar to that for the primary analysis of the primary endpoint (see Section 4.1.1.1). However, the study baseline of the analyzed TETRAS score [i.e., TETRAS Performance dominant UL score (Score no. 5 in

¹⁴ For definition of study baseline see beginning of Section 4.

[Appendix 8.1](#)) or TETRAS ADL UL score (Score no. 2 in [Appendix 8.1](#)), as applicable] will be used for baseline adjustment. Handling of multiplicity is addressed in Section [4.7.2](#).

Missing data handling, pooling of study sites, exploratory sensitivity analyses (Section [4.1.1.2](#)), and supplementary analyses (Section [4.1.1.3](#)) will also be handled analogously to the respective analyses of the primary endpoint. For ANCOVA-based sensitivity analyses, the respectively analyzed TETRAS subscale score (see above) will be used. The multiple imputation based sensitivity analysis was planned to be performed in case of more than 10% missingness on the respective key secondary endpoint among all treated subjects. During the DRM performed on 17Jan2024 under double blind conditions, the two key secondary efficacy endpoints were found to be completely available for all treated subjects. It was hence concluded that multiple imputation is not required for key secondary endpoints.

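### Sensitivity analysis no. 4 leaves two informative, already collected variables out of the Week 6 imputation; adding them is a cheap improvement, mainly against possible bias

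*Protocol*

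**What the plan says.** The primary analysis uses observed cases and assumes data missing at random (SAP 4.1.1.1). If more than 10% of primary endpoint values are missing in either arm, sensitivity analysis no. 4 applies multiple imputation to all subjects treated in Cycle 1. The other three sensitivity analyses (per protocol set, treatment by pooled site, gender and age) do not address missing data.

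The protocol fixes the imputation variables in Section 12.4.1.1: "Variables considered will comprise maximum tremor amplitude from previous visits including study baseline, treatment, study site, gender, and age". SAP 4.1.1.2, footnote 12, makes this explicit by naming "study baseline and Week 4 (V3) values for imputation of missing values at Week 6 (V4"). The printed code imputes Week 4 with "FCS REG(V3VAL = TRT01P SITEID SEX AGE BASE"), so Week 6 does not inform a missing Week 4 value, although the SAP chooses the method for arbitrary missing-data patterns. The `VAR` list holds treatment, site, sex, baseline, Week 4 and Week 6. It contains no TETRAS score and no Week 8 amplitude. Age is in the text and in both `FCS REG` lists but not in `VAR`.

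On the omitted data, SAP 4.1.2.1 reports that at the blinded review of 17 January 2024 "the two key secondary efficacy endpoints were found to be completely available for all treated subjects". One of these endpoints is the change in TETRAS Performance dominant UL score, so both its baseline and Week 6 values exist. Protocol Table 5 schedules the dominant-arm kinematic assessment at every Cycle 1 visit, Week 8 included.

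**The concern.** An imputation under missing at random is only as credible as the variables it conditions on. Suppose a recording is lost for a reason linked to the state of the arm at Week 6. The planned model sees that state only through baseline and Week 4. The Week 6 TETRAS score rates the same limb at the same visit. The Week 8 amplitude comes two weeks later, after the same single injection. Both carry information on the missing value and neither is used.

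The gap is widest when the baseline kinematic set is incomplete. SAP 4.1.1.1 requires every axis, task and round at baseline in order to select the task. SAP 4.1.3 then treats every post-baseline value for that task as missing. Footnote 10 of SAP 4.1.1.2 says Week 6 must be imputed even when its own recordings are complete. For such a subject the planned model works from treatment, site, sex and (by the text) age, with no measure of tremor severity, although TETRAS is available.

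**Working it through.** **1. The plan's own figure.** Inputs: "a treatment effect of about one standard deviation might be expected" (Protocol 12.1); "Assuming a 5% type I error and a randomization ratio of 2:1" (Protocol 12.1); "If not otherwise specified, statistical tests will be conducted 2-sided at type I error rate 5"% (SAP Section 4). For a two-sample t-test the noncentrality is (δ/SD)/√(1/n₁ + 1/n₂).

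- 34 + 17 = 51: 1/√(1/34 + 1/17) = 3.37 on 49 df, power 91.0%.
- 32 + 16 = 48: 1/√(1/32 + 1/16) = 3.27 on 46 df, power 89.2%.

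This reproduces the statement that "a total sample size of 51 analyzable subjects is required to achieve 90% power". It sets the scale used below: an effect of 1 SD, with about 75 subjects randomised 50:25.

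**2. What is collected and what is used.**

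| Variable | Completeness stated? | In planned model |
|---|---|---|
| Baseline amplitude | no | yes |
| Week 4 amplitude | no | yes |
| Week 8 amplitude | no | no |
| TETRAS Performance dominant UL, baseline and Week 6 | complete for all treated | no |

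**3. Baseline kinematics incomplete.** With no usable amplitude, the residual SD of the Week 6 value is 1.00 in standardised units. Conditioning on Week 6 TETRAS with correlation ρ reduces it to √(1 − ρ²). For assumed ρ of 0.3, 0.6 and 0.8 this gives 0.95, 0.80 and 0.60. Week 8 amplitude cannot help here, because it is underivable for the same reason.

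**4. Precision.** The documents give no correlations, so all of these are assumptions: Week 4 to Week 6 and Week 6 to Week 8 amplitude 0.70 or 0.85; baseline to later amplitude 0.6; same-visit TETRAS with amplitude 0.3, 0.6 or 0.8; missing proportion 12% (just above the trigger) or 25%. The simulation used 800 trials per scenario, 15 sites of 5, 40 imputations, and ANCOVA on treatment, site and baseline with a common variance (a simplification of the SAP model). Results were combined by Rubin's rules, T = W + (1 + 1/m)B. The enriched model adds baseline and Week 6 TETRAS and Week 8 amplitude. SE of the treatment difference (baseline-adjusted SDs), values missing completely at random:

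| Amplitude / TETRAS correlation | 12% missing, planned → enriched | 25% missing, planned → enriched |
|---|---|---|
| 0.70 / 0.3 | 0.270 → 0.270 | 0.303 → 0.302 |
| 0.70 / 0.6 | 0.272 → 0.268 | 0.303 → 0.295 |
| 0.85 / 0.6 | 0.263 → 0.260 | 0.283 → 0.276 |
| 0.70 / 0.8 | 0.271 → 0.263 | 0.303 → 0.285 |

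The largest reductions are (0.271 − 0.263)/0.271 = 3.0% and (0.303 − 0.285)/0.303 = 5.9%. Neither model shows material bias in this setting.

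**5. Bias when loss depends on Week 6 TETRAS.** Same simulation; difference from the full-data estimate in absolute value:

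| Mechanism | Planned | Enriched |
|---|---|---|
| Same dependence in both arms (12% and 25%) | 0.00–0.07 SD | within 0.01 |
| NT 201 arm only (12% and 25%) | 0.02–0.10 SD | within 0.01 |
| Opposite directions by arm (12%) | 0.05–0.15 SD | within 0.01 |

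**6. Bias when loss depends on the Week 6 amplitude itself.** A separate simulation used 1,500 trials, 20 imputations, 50 versus 25, about 15% missing, poor responders on NT 201 more often unrecorded, and mid-range correlations. The mean estimates were −0.996 with full data, −1.092 with complete cases, −1.045 with planned imputation and −1.027 with enriched imputation. The biases are therefore 0.096, 0.049 and 0.031 SD. Enrichment removes 0.018 SD of the bias left by the planned model. The rest remains, because no missing-at-random model removes it fully.

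**The case against.** The case for leaving the plan alone has several sound parts.

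- **Low stakes.** The analysis is exploratory, conditional on the 10% trigger, and read descriptively only. The SAP does not say the trigger was met for the primary endpoint. This stands.
- **Losses may be technical.** Any missing axis, round or task makes the endpoint missing. TETRAS Performance is not among the assessments done at remote visits, so its completeness at Week 6 points to recording failures more than drop-out. If so, there is little bias to remove. This stands as a possibility; the documents do not give the reasons.
- **The favourable scenarios are chosen.** The 0.15 SD figure arises when loss depends on TETRAS in opposite directions by arm, and adding TETRAS removes that bias by construction. This stands, and that figure is an upper end, not an expectation.
- **The baseline gap may be rare.** The SAP takes the last valid pre-injection value, so screening kinematics can stand in for the baseline visit. This narrows the problem but does not close it: footnote 10 provides for exactly this case.
- **TETRAS completeness was not known when the protocol was written.** True, but the SAP is dated 24 January 2024, a week after the review.

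A reader might infer that the plan discards the strongest predictors. The documents do not support that. Week 4 is as close to Week 6 as Week 8 is, and it is kept. The TETRAS score sums kinetic, spiral, handwriting and dot tasks as well as postural tremor, so it does not observe wrist amplitude directly. A reader might also infer a real loss of precision from the omission. Residual variance of a single imputed value can fall noticeably under assumed correlations, but the treatment estimate hardly moves (step 4).

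**Conclusion.** The point holds as a cheap improvement to the one missing-data check on the primary endpoint. The planned imputation is a recognisable missing-at-random model, but it leaves out a same-visit rating known to be complete and a nearby amplitude. It also has no severity information on subjects whose baseline kinematics are incomplete.

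The benefit to precision is small: about 0–3% of the SE at 12% missing and 0–6% at 25%. The main benefit is protection against a possible bias. That bias is about 0.05 SD reduced to 0.03 SD if loss depends on Week 6 amplitude, and up to 0.15 SD removed in the most adverse TETRAS-dependent scenario. If losses are purely technical, the gain is close to nil. Every size rests on assumed correlations, missing proportions and mechanisms.

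It would be wrong to read this as a flaw in the confirmatory test, which is unaffected, or as evidence that the planned imputation is biased. The documents do not show why values are missing. Richer predictors also only strengthen a missing-at-random analysis; they do not replace a check under missing not at random, and none is planned.

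**What to change.** In Protocol 12.4.1.1 and SAP 4.1.1.2 no. 4, add as auxiliary variables the TETRAS Performance dominant UL score at study baseline and at Week 6, and the Week 8 (V5) amplitude for the task selected at study baseline.

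In the `PROC MI` call:

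- put these three variables and `AGE` in `VAR`, since opening up the predictor lists without adding `AGE` would drop a variable the protocol requires;
- let each incomplete variable be imputed from all the others, so that Week 6 and Week 8 also inform a missing Week 4 value;
- set the `MINIMUM` and `ROUND` slots to suit each variable, with no whole-unit rounding of TETRAS, which is scored in 0.5 steps.

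Leave the ANCOVA on the completed datasets unchanged and record the change in SAP Section 6.

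The cost is a few lines of text and code. All the data are already scheduled for collection and derivation. The downside is a slightly larger imputation model with about 75 subjects and about 15 site levels.
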